6.1 Population characteristics

6.1.1 Disposition of Subjects

The following will be tabulated overall and/or by treatment group:

- Study sample sizes (FAS, PPS LVEF, PPS BNP, SAF and PKS)
- Study sample sizes by region, country, and site
- Subject disposition
- Number of subjects and primary reasons for screening failures (only overall)
- Number of subjects and primary reasons for permanent discontinuation of study medication (by treatment group and overall for FAS and SAF)
- Number of subjects and primary reasons for discontinuation from study (by treatment group and overall for FAS and SAF)

6.1.2 Demographic and Baseline Characteristics

Descriptive summaries of demographics and baseline characteristics will be presented by treatment group and overall for the PPS LVEF, PPS BNP, FAS and SAF populations. Comparability of the treatment groups with respect to demographics and baseline characteristics will be assessed using the descriptive summaries. Same analyses will also be performed for subjects who prematurely discontinue study participation or intake of study medication.

The following demographic data will be summarized:

- Age at baseline (years);
- Age category: <65, 65-75, >75 years;
- Gender (male vs. female)
- Race and ethnicity;
- Height (cm);
- Weight (kg) at baseline;
- BMI (kg/m²);
- BMI category: ≤30 vs. >30 kg/m²;
- Tobacco smoking history
- Alcohol consumption history
- Recent caffeine-containing beverage and chocolate consumption history

The following baseline characteristics will be summarized:

- LVEF(%) at baseline: ≤ 25 vs. > 25
- LVEF(%) at baseline: ≤ 40 vs. > 40
- LVEF(%) at baseline: ≤ 45 vs. > 45
- LVEF(%) at baseline: \leq mean vs. $>$ mean
- NT-proBNP (pg/ml) at baseline: \leq median vs. $>$ median
- NYHA class at baseline: II vs. III / IV
- Prior β -blocker: yes vs. no
- Region: North America / West Europe / East Europe / Asia
- Region: Japan vs. rest-of-the-world (analysis to be included in reports specific for Japan only)
- Time of CHF diagnosis to randomization (months): ≤ 3 vs. > 3
- Prior hospitalization for heart failure: yes vs. no
- Etiology of CHF: ischemic vs. non-ischemic
- Diabetes: yes vs. no
- Atrial fibrillation: yes vs. no
- Hypertension: yes vs. no
- Prior CHF medication:
 - Prior β -blocker in max tolerated dose: yes vs. no
 - Prior use of ivabradine: yes vs. no
 - Prior use of MRA: yes vs. no
 - Prior use of ACE inhibitor: yes vs. no
 - Prior use of ARB: yes vs. no
 - Prior use of angiotensin receptor-neprilysin inhibitor (ARNI): yes vs. no
- Estimated GFR (ml/min/1.73 m²): ≤ 60 vs. > 60

6.1.3 Medical history

Medical history findings will be summarized using medical dictionary for regulatory activities (MedDRA, version refers to TS domain) terms for the FAS population by treatment group.

6.1.4 Prior and Concomitant Medications

All non-study medications taken during the study will be coded using the World Health Organization Drug Dictionary (WHO-DD) in its latest version which is specified in the TS domain and the Anatomical Therapeutic Chemical (ATC) classification system. Coding will include the drug class and preferred drug name.

Non-study medications taken during the study will be categorized as prior medications, concomitant medications during the treatment period, and post treatment medications during the safety follow-up.

Prior medications will be defined as a non-study medication with a stop date prior to the first dose of study treatment.

Concomitant medications will be defined as:

- Non-study medications with a start or stop date on or after the date of the first dose of study treatment;
- Non-study medications that started prior to the first dose of study treatment and are ongoing during the treatment period;
- Non-study medications with partial start dates that indicate that the medication could be concomitant in relation to the date of the first dose of study treatment;
- Non-study medications with completely missing start dates, unless their stop dates confirm otherwise (i.e. the stop date is before the first dose of study treatment).

Post treatment medications are defined as non-study medications taken up to 6 weeks after the last study medication intake.

All concomitant medications will be listed, including verbatim descriptions and coded terms, and flags for prior medications. Prior, concomitant, and post treatment medications will be summarized using frequencies of subjects reporting each drug category and preferred drug name. Additionally

- concomitant medications of interest required by the HF guideline, i.e. ACEI/ARB/ARNI, MRA, beta blockers and/or Ivabradine and their combinations
- other medications of interest relevant to the cardiovascular system, i.e. digitalis glycosides, loop and thiazide diuretics, Potassium sparing agents (excluding MRAs), Statins, anticoagulants, antiplatelets, natriuretic peptides, soluble guanylate cyclase stimulators, GLP-1 antagonists, insulins, and SGLT-2 inhibitors,

will be summarized using frequencies of subjects reporting each preferred drug name at baseline and post-baseline. Frequency of subjects who experienced dose increase, dose decrease or no dose change of concomitant medication of interested required in the HF guideline will also be summarized.

For each subject, multiple records of the same concomitant medication will be counted once within a drug class and preferred name.

6.2 Efficacy

6.2.1 Primary efficacy variables and analyses

6.2.1.1 Primary efficacy variables

- Absolute change from baseline in left ventricular ejection fraction (LVEF; %) after 20 weeks measured by echocardiography, i.e., LVEF at week 20 minus LVEF at baseline.
- Absolute change from baseline in log-transformed NT-proBNP (pg/mL) after 20 weeks, i.e., log-transformed NT-proBNP at week 20 minus log-transformed NT-proBNP at baseline.

6.2.1.2 Primary analysis of primary efficacy variables

Primary analysis will be performed in PPS LVEF and PPS BNP respectively, a subset of the FAS comprising “compliant and adherent” patients (as much as possible, defined via validity criteria). To avoid bias, the PPS LVEF and PPS BNP will also include those “compliant and adherent” patients who are “censored” due to CV death or a hospitalization for HF preventing the assessment of the relevant efficacy endpoints 20 weeks after randomization to take place as planned. For missing post-baseline value due to CV death or study drug/study discontinuation due to HF, a worst case approach (WOV) will be applied. The worst change by treatment group will be calculated. If the worst change in that treatment group is positive for LVEF / negative for NT-proBNP, the worst case in that treatment group is 0. The missing change from baseline value will be imputed with a multiple 1.0 of the median of worst changes from baseline value among all treatment groups. The post-baseline value at week 20 will be calculated accordingly as baseline value + imputed change from baseline. If this imputed post-baseline value for LVEF is < 0% in case of CV death preventing the measurement, then the post-baseline value will be replaced with 0 and the imputed change from baseline will be modified to (- baseline value). Similarly, if the imputed post-baseline value is < 5% in case of a hospitalization for HF and no CV death preventing the measurement, the post-baseline value will be set to 5% and the corresponding imputed change from baseline will be reset to (5 - baseline value).

For both primary efficacy variables, it is planned to perform a test for a dose-response signal, respectively, under the assumption of a nearly monotone dose-response relationship in the dose range considered. The MCP-Mod method (5) combining multiple comparison procedures (MCP) principles with modeling techniques will be used for the primary statistical analysis of the primary efficacy variables. This method allows the flexibility of modeling for dose estimation, while preserving the robustness to model misspecification associated with MCP procedures. The MCP-Mod method will be used based on SAS programs provided (9) and the results may be validated within R (10) with the actual DoseFinding package (11).

Two primary variables have been defined to better evaluate multiple dimensions of the treatment effect, thereby adding a source of multiplicity. The overall outcome of the primary efficacy analysis will be considered positive if at least one of the two null hypotheses related to the primary efficacy variables can be rejected. The Hochberg (step-up) procedure will be applied to control the family-wise error rate (FWER):

Consider the null hypotheses for LVEF, $H_{0,LVEF}$, and for NT-proBNP, $H_{0,NT-proBNP}$, and their associated raw p-values p_{LVEF} and $p_{NT-proBNP}$. The Hochberg test is performed using the following steps:

1. If $\max(p_{LVEF}, p_{NT-proBNP}) \leq \alpha = 0.05$, both null hypotheses $H_{0,LVEF}$ and $H_{0,NT-proBNP}$ will be rejected and the procedure stops.
2. If $\max(p_{LVEF}, p_{NT-proBNP}) > \alpha = 0.05$ and $\min(p_{LVEF}, p_{NT-proBNP}) \leq \alpha/2 = 0.025$, we will fail to reject the null hypothesis related to the larger p-value $\max(p_{LVEF}, p_{NT-proBNP})$ and the null hypothesis related to the smaller p-value $\min(p_{LVEF}, p_{NT-proBNP})$ will be rejected.
3. Otherwise, we will fail to reject both null hypotheses $H_{0,LVEF}$ and $H_{0,NT-proBNP}$.

Assumptions

Five active doses of neladenoson bialanate will be used in this study: 5 mg, 10 mg, 20 mg, 30 mg, and 40 mg, as well as a placebo arm corresponding to a 0 mg dose.

The measurements of the primary efficacy variables are assumed to be normally distributed with the same standard deviation σ and independent between patients, respectively.

LVEF: The following assumptions were made for the absolute change from baseline in LVEF over 20 weeks:

- the expected mean effect under the placebo dose is conservatively assumed as an absolute increase from baseline of up to $\Delta = 2\%$ with a standard deviation of $\sigma = 7\%$
- while the maximum observable mean effect under neladenoson bialanate within the dose range considered is assumed as an absolute increase of $\Delta = 5\%$ with a standard deviation of $\sigma = 7\%$.

This results in an expected maximum effect size of $(5-2)/7 = 3/7 = 0.43$ under conservative assumptions. Note that the threshold of clinical relevance is an absolute difference of 3% in the change from baseline over the placebo control group.

NT-proBNP: The following assumptions were made for the absolute change from baseline in the log-transformed NT-proBNP over 20 weeks:

- the expected mean effect under the placebo dose is assumed as an absolute decrease from baseline of $-0.105 \log(\text{pg/mL})$ with a standard deviation of $\sigma = 0.85 \log(\text{pg/mL})$, which is equivalent to a 10% relative reduction from a mean of 2,500 pg/mL at baseline.
- while the maximum observable mean effect under neladenoson bialanate within the dose range considered is assumed as an absolute decrease from baseline of $-0.357 \log(\text{pg/mL})$ with a standard deviation of $\sigma = 0.85 \log(\text{pg/mL})$, which is equivalent to a 30% relative reduction from a mean of 2,500 pg/mL at baseline.

It is assumed that the respective primary response efficacy variable, denoted as Y , is observed for the 6 parallel groups corresponding to doses levels: (placebo =) $d_1 < d_2 < \dots < d_k$, where $k = 6$.

For patient j within treatment group i the response can then be described by the following model:

$$Y_{ij} = f(d, \theta) + \varepsilon_{ij}, \quad \varepsilon_{ij} \sim N(0, \sigma^2), \quad i = 1, \dots, k, \quad j = 1, \dots, n_i,$$

[figure not shown]
where $f(\cdot)$ is parameterized by a vector of parameters θ and ε_{ij} is the error term.

A candidate set with $M=5$ different dose response shapes $f(\cdot)$ based on four models was chosen for the MCP-Mod method. Table 6–1 displays the response expressions for the shapes in the candidate sets for both, change in LVEF and change in log-transformed NT-proBNP. Figure 6–1 shows the corresponding dose-response shapes for change in LVEF. The model parameters were obtained through discussions with experts in the clinical team, taking prior beliefs and uncertainty into account. The dose-response shapes for NT-proBNP are equivalent to those for LVEF but with decreasing trends.

Table 6–1: Dose-response shapes used in the candidate set

Model	Response as function of dose d	
	LVEF	NT-proBNP
Linear	$2 + 0.075d$	$-0.105 - 0.0063d$
Sigmoidal E_{\max} 1	$2 + 3.007689d^4 / (9^4 + d^4)$	$-0.105 - 0.2526d^4 / (9^4 + d^4)$
Sigmoidal E_{\max} 2	$2 + 3.375d^3 / (20^3 + d^3)$	$-0.105 - 0.2835d^3 / (20^3 + d^3)$
E_{\max}	$2 + 3.09375d / (1.25 + d)$	$-0.105 - 0.2599d / (1.25 + d)$
Quadratic	$2 + 0.2d - 0.00333d^2$	$-0.105 - 0.0168d + 0.00028d^2$

Figure 6–1: Dose-response shapes used in the candidate set for change in LVEF

Based on the standardized versions of the models in the candidate set and the sample size allocation planned for this study, the optimum contrast coefficients for the 5 contrast tests on the dose-response shapes can be derived for both primary variables (Table 6–2).

These contrast coefficients will be updated based on the actual number of subjects per treatment group which are finally available for the analysis.

Table 6–2: Contrast coefficients

Model	Contrast coefficients for dose					
	0.0	5.0	10.0	20.00	30.00	40.00
Linear	-0.674	-0.159	-0.186	0.077	0.340	0.603
Sigmoidal E _{max} 1	-0.784	-0.223	0.004	0.315	0.342	0.347
Sigmoidal E _{max} 2	-0.615	-0.197	-0.290	0.130	0.423	0.550
E _{max}	-0.901	0.046	0.170	0.215	0.231	0.240
Quadratic	-0.815	-0.129	-0.024	0.288	0.392	0.288

Analysis

Step 1: Detection of dose-response signal

For detecting an overall trend, or a dose-response signal, each of the M=5 dose-response shapes in the candidate set will be tested, using a single contrast test based on the updated version of contrast coefficients taking the actual sample sizes per treatment group into account.

For each model m , $m = 1, \dots, 5$, in the candidate set

the null hypothesis $H_{0m}: c_m \mu_m^0 = 0$

will be tested against

the respective 1-sided alternative hypothesis $H_{1m}: c_m \mu_m^0 > 0$,

where $\mu_m^0 = (\mu_{m1}^0, \dots, \mu_{m6}^0)' = (f_m^0(d_1, \theta_m^0), \dots, f_m^0(d_6, \theta_m^0))'$ and

f^0 is the standardized version of the dose-response model $f(d, \theta) = \theta_0 + \theta_1 f^0(d, \theta^0)$. In this parameterization, θ_0 is a location parameter and θ_1 is a scale parameter such that only θ^0 determines the shape of the model function.

The contrast coefficients $c_{m1} \dots c_{m6}$ for the m -th model are chosen such that they maximize the power to detect the underlying model. These optimal contrast coefficients depend only on the parameters in the standardized model function θ^0 , which determine the model shape (5) and the actual group sample sizes (which is known after unblinding of the study). The i th member of the optimal contrast vector $c_{opt,m}$ for testing the shape model m is proportional to

$$n_i(\mu_{mi}^0, \dots, \bar{\mu}), i = 1, \dots, 6,$$

where $\bar{\mu} = N^{-1} \sum_{i=1}^6 \mu_{mi}^0 n_i$. In case of unequal sample sizes per treatment arm, $c_{opt,m}$ cannot be expressed in closed form and numerical optimization techniques are required (9, 11). The $c_{opt,m}$ is derived by fulfilling the condition $\sum_{i=1}^6 c_{mi}^2 = 1$.

The single contrast test for detecting the m -th model shape is defined by

$$T_m = \frac{\sum_{i=1}^6 c_{mi} \bar{Y}_i}{s \sqrt{\sum_{i=1}^6 c_{mi}^2 / n_i}}, m = 1, \dots, 5, \quad \text{where } S^2 = \frac{\sum_{i=1}^6 \sum_{j=1}^{n_i} (Y_{ij} - \bar{Y}_i)^2}{N-6}.$$

Under the null hypothesis of no dose-response effect, i.e. $\mu_{d_1} = \dots = \mu_{d_6}$, the test statistic $T = (T_1, \dots, T_5)'$ follows a central multivariate t distribution with N-6 degrees of freedom and correlation matrix $R = (\vartheta_{ij})$, where $\vartheta_{ij} = \frac{\sum_{l=1}^6 c_{il} c_{jl} / n_l}{\sqrt{\sum_{l=1}^6 c_{il}^2 / n_l \sum_{l=1}^6 c_{jl}^2 / n_l}}$.

The final test statistic T_{max} is based on the maximum contrast test and a “proof-of-concept” dose-response relationship is detected if this maximum statistic T_{max} , and thus at least one single contrast test, is statistically significant, while controlling the familywise error rate at level α . If $q_{1-\alpha}$ denotes the multiplicity adjusted critical value, a dose-response signal is established if $T_{max} \geq q_{1-\alpha}$. The smallest of the corresponding adjusted p-values will be used for the Hochberg test.

This analysis will be performed for the FAS and PPS LVEF, PPS BNP populations respectively, where the PPS LVEF and PPS BNP analysis is the primary analysis.

If no candidate model is statistically significant, the procedure stops, indicating that a dose-response relationship cannot be established from the observed data.

Out of the statistically significant models in the candidate set a best model can be selected for the next step: modeling and estimation.

Step 2: Modeling and estimation of target doses

If a dose-response signal is established, the selected dose-response model(s) will be fitted to the observed data to estimate the model parameters.

The estimated dose-response model will be plotted against the doses including 90% confidence bands. Once the dose-response model has been successfully fitted to the data, target dose(s) of interest are estimated. Given a clinically relevant effect Δf , a minimum effective dose (MED_{Δ}) associated with model $f(d, \theta)$ is defined as

$$MED_{\Delta} = \operatorname{argmin}_{d \in (d_1, d_6]} \{f(d, \theta) \geq f(d_1, \theta) + \Delta\}.$$

Estimates of MED_{Δ} will be calculated for a clinically relevant change in LVEF assumed as $\Delta \text{wil}\%$ and potentially a plausible range of Δ values which will be defined based on the observed data. Estimation for change in log-transformed NT-proBNP will be performed analogously, ensuring an adequate back-transformation to allow for better interpretability of the results. In addition, estimates considering confidence bounds for the predicted value at a certain dose may be used. The final choice of the target dose depends on the evaluation of the primary efficacy variables and other efficacy variables, as well as safety considerations.

Additionally LVEF and increasing change from baseline, NT-pro-BNP and decreasing change from baseline, and log-transformed NT-proBNP and decreasing change from baseline will be descriptively summarized by treatment and overall, and visit in PPS LVEF and PPS BNP respectively.

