6.4 Withdrawal of patients from study

6.4.1 Withdrawal

This section was changed in Amendment 2, see Section 15.1 for details.

An excessive rate of withdrawals (either patients discontinuing study medication or study withdrawal) can render the study non-interpretable. Therefore, un-necessary withdrawal of patients should be avoided and all efforts should be taken to motivate patients to comply with all the study specific procedures and to be followed until the end of the trial to detect the occurrence of cardiovascular events / assess vital status.

Before permanently discontinuing study medication (either initiated by the patient or the investigator) an interruption should be considered. Patients, who have temporarily discontinued study medication for any reason, should restart as soon as medically justified in the opinion of the investigator; the patient can re-start at any time before the end of treatment

(EOT) visit. In addition, patients should not be withdrawn from the study drug or from the study solely due to reaching a potential cardiovascular event.

All patients who permanently discontinue study medication should come in for the EOT / premature discontinuation visit as soon as possible after discontinuation of the study medication and the safety follow-up visit 4 weeks after the last dose. In addition, they will be contacted by the investigator via the scheduled Week 26 phone call to assess occurrence of cardiovascular events.

The investigator should show due diligence and explore all possible options to reach a patient who fails to return to a visit. The site must document all attempts to try to contact the patient in the medical records / source documents.

In order to avoid loss-to-follow-up, the investigator should ask the patient at the study start for the contact details of a relative or friend who can be contacted in case the patient cannot be reached.

Patients should not be withdrawn from follow-up unless the patient explicitly withdraws consent to be contacted. All efforts should therefore be made to minimize the number of patients who withdraw such consent as, in general, no further information on cardiovascular events and survival status may be collected after that point.

Withdrawal criteria

Patients **must be withdrawn from the study** if any of the following occurs:

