The primary efficacy analysis aims at evaluating the dose-response relationship of the primary and secondary efficacy variables (except for clinical outcomes) for all randomized patients who have remained in the study and adhered to study treatment according to the study protocol until Week 20 (“completers and treatment adherers” analysis). Therefore, the primary analysis will be performed in the per-protocol set, a subset of the FAS comprising “compliant and adherent” patients (as much as possible, defined via validity criteria). To avoid bias, the PPS will also include those “compliant and adherent” patients who are “censored” due to CV death or a hospitalization for HF preventing the assessment of the relevant efficacy endpoints 20 weeks after randomization to take place as planned. It is expected that these are the only patients for whom missing observations need to be considered in the primary analysis. A “worst case” approach will be used, where the missing change from baseline value will be imputed with a multiple of the worst change from baseline value, which is possible given the individual baseline value observed in the respective treatment group, or 0 if the worst change in that treatment group is positive for LVEF / negative for NT-proBNP.

As a sensitivity analysis, a “completers and treatment adherers” only analysis excluding the censored patients in the per-protocol analysis set will be performed. This strategy leads to unbiased estimates only if missing values are “missing completely at random” (MCAR), i.e. the missingness – including missing data due to death – is independent of both observed and unobserved outcomes. This condition is unlikely to hold exactly but rather approximately.

Further sensitivity analyses on the PPS may be performed if the missing data patterns suggest further exploration.

Efficacy analysis using the FAS

The efficacy analysis in the FAS aims at evaluating the dose-response relationship of the primary and secondary efficacy variables for all randomized patients. Efficacy analyses in the FAS will include the following:

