5.1 Assignment of analysis sets

Final decisions regarding the assignment of subjects to analysis sets will be made during the review of study data and documented in the final list of important deviations, validity findings and assignment to analysis set(s) (see section 4.6).

Data for all patients who signed informed consent but were not randomized will not be included in any statistical analyses except standard disposition tables and listings provided in the clinical study report (Screening failures and discontinued patients).

The statistical analysis sets are defined as follows:

Full analysis set (FAS)

The FAS population consists of all randomized unique patients. According to the ICH E9 guideline, this analysis set is as complete as possible and as close as possible to the intent-to-treat (ITT) ideal. Patients will be analyzed as randomized. The FAS will be used to display baseline characteristics and to display efficacy analyses. Sensitivity analyses are based on the FAS population. For the analyses conducted in FAS, patients will be analyzed as randomized per IxRs.

Safety analysis set (SAF)

The SAF population consists of all randomized patients who received at least one dose of study medication after randomization. The SAF will be used to display safety analyses. For analyses conducted in SAF, patients will be analyzed as treated.

Per-protocol set (PPS)

The protocol defines a PPS. Since there are two primary efficacy variables, we will define PPS LVEF and PPS BNP, specific to the presence of non-missing data for each variable separately.

Per-protocol set for LVEF (PPS LVEF): The PPS LVEF population consists of all FAS population patients without validity findings. Validity findings may include adherence and compliance issues and the violation of inclusion / exclusion criteria affecting efficacy evaluation. If the left ventricular ejection fraction of this subject is measured after first dose of study medication but within a specified time frame this subject will not be excluded from PPS LVEF. The patients with invalid/missing baseline value or missing post-baseline value not due to CV death or HF hospitalization will be excluded from the PPS LVEF. The primary analysis of LVEF will be conducted in PPS LVEF.

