Per-Protocol set for NT-proBNP (PPS BNP): The PPS BNP population consists of all FAS population patients without validity findings. Validity findings may include adherence and compliance issues and the violation of inclusion / exclusion criteria affecting efficacy evaluation. If the NT-proBNP (pg/mL) of this subject is measured after first dose of study medication but within a specified time frame this subject will not be excluded from PPS BNP. The patients with invalid/missing baseline value or missing post-baseline value not due to CV death or HF hospitalization will be excluded from the PPS BNP. The primary analysis of NT-proBNP will be conducted in PPS BNP.

A list of potential validity findings will be provided in a separate important deviations and validity specifications document which will be finalized before database lock. The detailed definitions and the assignment of patients to this analysis set will be based on the validity review meeting. Patients will be analyzed as treated.

Pharmacokinetic analysis set (PKS)

The PKS population consists of all patients treated with neladenoson bialanate with at least 1 valid BAY 84-3174 plasma concentration and without protocol deviation that would interfere with the evaluation of the PK data.

6. Statistical Methodology

The formal statistical analyses will be both descriptive and inferential. Summaries will be provided for each of the treatment group. All of analyses planned in this SAP will be repeated in Japanese subjects only.

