6.2.1.3 Secondary analysis of primary efficacy variables

As a secondary analysis pairwise comparisons of the active neladenoson bialanate dose groups with the placebo group will be performed without controlling the family-wise error rate, by calculating the 90% confidence interval for the difference in primary efficacy variable between each active dose of neladenoson bialanate and placebo.

6.2.1.4 Sensitivity analyses of primary efficacy variables**6.2.1.4.1 Sensitivity analysis of primary efficacy variables in PPS LVEF and PPS BNP**

As a sensitivity analysis, primary analysis of primary efficacy variables on the “completers and treatment adherers” excluding the censored patients in the per-protocol analysis set will be repeated. This strategy leads to unbiased estimates only if missing values are “missing completely at random” (MCAR), i.e. the missingness – including missing data due to death – is independent of both observed and unobserved outcomes. This condition is unlikely to hold exactly but rather approximately.

Further sensitivity analyses on the PPS LVEF and PPS BNP may be performed if the missing data patterns suggest further exploration.

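### The worst-case imputation trigger in SAP 6.2.1.2 is discontinuation due to HF, but PPS membership, the 5% LVEF floor and protocol 10.3.3 all use HF hospitalization

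*SAP*

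**What the plan says.** SAP 6.2.1.2 first keeps in the two per-protocol sets the adherent patients whose Week 20 assessment was prevented by CV death or an HF hospitalization. The next sentence says when a value is imputed: "For missing post-baseline value due to CV death or study drug/study discontinuation due to HF, a worst case approach (WOV) will be applied". Later in the paragraph, the 5% lower limit on an imputed LVEF applies "in case of a hospitalization for HF and no CV death preventing the measurement".

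The other places that govern the same patients read as follows.

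- **Protocol 10.3.3:** the PPS includes patients censored "due to CV death or a hospitalization for HF preventing the assessment of the relevant efficacy endpoints 20 weeks after randomization", and worst-case imputation is prescribed for them. It adds: "It is expected that these are the only patients for whom missing observations need to be considered in the primary analysis".
- **SAP 5.1, PPS LVEF:** patients with a "missing post-baseline value not due to CV death or HF hospitalization will be excluded from the PPS LVEF".
- **SAP 5.1, PPS BNP:** patients with a "missing post-baseline value not due to CV death or HF hospitalization will be excluded from the PPS BNP".
- **SAP 6.2.1.4.2 (FAS) and SAP 6.2.2.2 (secondary variables):** both use CV death or HF hospitalization. The second applies the same named method, WOV.
- **SAP 6.2.1.4.1:** the primary analysis, "excluding the censored patients in the per-protocol analysis set will be repeated".
- **Protocol 6.4.1:** "patients should not be withdrawn from the study drug or from the study solely due to reaching a potential cardiovascular event".

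**The concern.** Discontinuing because of HF and being hospitalized for HF are different events. Protocol 6.4.1 asks sites to keep hospitalized patients on drug and in the study, so hospitalization without discontinuation is what the protocol aims for. HF events without hospitalization also exist, since protocol 9.4.3.1 collects urgent HF visits separately.

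The sentence with the discontinuation wording is the only one that says when a primary endpoint is imputed, so it is the one a programmer would code. If it is coded as written, a hospitalized patient who has not discontinued and has no Week 20 value gets no worst-case value and drops out of the contrast. For these patients the primary analysis then equals the SAP 6.2.1.4.1 sensitivity analysis, which can no longer show what imputing them does. Imputed values lie far from the arm means, so a few patients can move the primary p-value.

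**Working it through.** **1. Passages side by side**

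| Rule | Place | Condition besides CV death |
|---|---|---|
| Censored patients kept in the PPS | Protocol 10.3.3; SAP 6.2.1.2 | HF hospitalization preventing the assessment |
| PPS LVEF and PPS BNP exclusion | SAP 5.1 | HF hospitalization |
| Imputation trigger, primary endpoints | SAP 6.2.1.2 | Drug or study discontinuation due to HF |
| 5% LVEF floor | SAP 6.2.1.2 | HF hospitalization |
| MNAR pattern in the FAS | SAP 6.2.1.4.2 | HF hospitalization |
| WOV trigger, secondary variables | SAP 6.2.2.2 | HF hospitalization |

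Two groups fall between the rules:

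- (a) Hospitalized for HF, not discontinued, no Week 20 value: in the PPS, but the trigger is not met.
- (b) Discontinued for HF without hospitalization, no post-baseline value: the trigger is met, but SAP 5.1 excludes the patient, so the trigger has no effect.

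Group (b) should be uncommon. Discontinuers are due an EOT/PDV visit with echocardiography and blood sampling (protocol 6.4.1 and 9.2.8), and may leave the PPS for non-adherence.

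**2. Reproducing the plan's figures**

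Inputs: LVEF SD 7; one-sided alpha 5%; the five shapes of SAP Table 6–1; PPS N = 0.75 × 384 = 288, split 72/24/48/48/48/48 over 0/5/10/20/30/40 mg. Contrasts proportional to n_i(μ_i − μ̄), scaled to unit sum of squares, match SAP Table 6–2 to within 0.001. The simulated critical value is about 1.965. Power for linear, sigmoidal Emax 1, sigmoidal Emax 2, Emax and quadratic is about 80/91/87/88/86%. Protocol Table 10–2 gives 80.31/91.39/87.30/88.25/86.09% at N = 288.

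**3. Size of an imputed value**

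Imputed change = median over the six arms of each arm's worst change, with an arm's worst set to 0 if it is an improvement. Mean over 20,000 simulated trials per shape:

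- LVEF: -11.97, -11.42, -11.99, -10.90, -11.42 points (same order of shapes).
- Log NT-proBNP (SD 0.85): +1.55 to +1.64.

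**4. Shift in an arm mean per patient switched from left out to imputed**

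Shift = (imputed value − arm mean) / n.

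- 40 mg, linear: (-11.97 − 5)/48 = -0.354
- 10 mg, sigmoidal Emax 2: (-11.99 − 2.38)/48 = -0.299
- Placebo, linear: (-11.97 − 2)/72 = -0.194
- 5 mg, Emax: (-10.90 − 4.47)/24 = -0.640

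Over all shapes the LVEF shift is 0.30–0.35 points in a 48-patient arm, 0.18–0.19 in placebo and 0.57–0.64 at 5 mg. The planned maximum difference is 5 − 2 = 3 points. For NT-proBNP it is 0.037–0.042 log units in a 48-patient arm, for example (1.64 + 0.357)/48 = 0.042, against a planned maximum of 0.357 − 0.105 = 0.252.

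**5. LVEF power, linear shape, contrasts recomputed for the actual n**

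| Group (a) patients (assumed) | Imputed | Left out |
|---|---|---|
| 1 / 2 / 4, all at 40 mg | 74 / 68 / 54% | 80 / 80 / 79% |
| 1 / 2 / 4, all on placebo | 84 / 88 / 93% | about 80% |
| 4: one each at 0, 10, 30, 40 mg | 75% | 79–80% |
| 12 in the ratio 3:1:2:2:2:2 | 72–73% | 79% |
| 2% of every arm | 76% | 80% |

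Over the five shapes, imputing one patient at 40 mg costs 2–6 power points and imputing four costs 12–25. The 0% and 5% floors were not applied, because the documents give no baseline LVEF distribution. With a change near -12, the 5% floor acts only for baselines below about 5 + 12 = 17%.

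**The case against.** The strongest reply is that the intended rule is clear. The sentence directly before defines the censored patients by HF hospitalization, the 5% floor makes sense only if hospitalized patients are imputed, and the SAP says that it is based on the protocol. On this view the phrase is loose shorthand. That is probably what was meant, but the text does not say so. The SAP 3.0 history entry records only more detail on worst-case imputation and gives no explanation of the wording.

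Second, group (a) is narrow. Patients kept on drug and in the study are those most likely to attend Week 20, and NT-proBNP needs only a blood sample. This stands: the group may be empty.

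Third, the low power figures are the cost of the intended imputation, and programming the sentence literally leaves power near 80%. This also stands. The defect is that the plan does not fix which of two analyses is the primary one. It is not a loss of power.

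Fourth, the single-arm scenarios are the extreme ones. Spread over arms the gap is smaller: four patients, one each at 0, 10, 20 and 30 mg, give about 78–79% imputed against 79–80% left out. Imbalance by arm cannot be excluded, however, in a trial whose drug could affect HF events.

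Finally, the FAS pattern-mixture analysis penalizes HF-hospitalized patients whichever reading is used. It is a partial backstop, with a different population and imputation, and it is not the primary test.

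**Conclusion.** The concern holds. The primary imputation trigger contradicts the plan's own definition of the patients it is meant to cover, and the literal rule leaves some PPS members without a value. The mismatch can be read from the text and rests on no assumption. Its numerical effect does rest on assumptions: the number and arm of the affected patients, the planning means and SDs, and floors not applied. Between imputing and leaving out, LVEF power under the linear shape differs by about 4 points if 2% of every arm is affected, and by up to 25 points for four patients in the 40 mg arm. In the placebo arm the effect runs the other way. With no affected patients there is no effect. It should be fixed before unblinding, because afterwards the choice between readings could be made knowing the result.

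**What to change.** In SAP 6.2.1.2, replace the reference to drug or study discontinuation due to HF with hospitalization for HF preventing the Week 20 assessment, so that it agrees with protocol 10.3.3, SAP 5.1 and the floor rule. If HF-related discontinuation was meant to count, add it instead to the PPS LVEF and PPS BNP definitions and to the floor rule, and record it as a change from the protocol. Either way, make the change in a dated SAP amendment before unblinding. The first option costs one phrase. Neither needs new data or more patients, and the sample size calculation is unaffected.
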